# 9.2 CTCAE Routine Reporting Requirements

In addition to the solicited adverse events listed in Section 9.1, the following table outlines the combinations of time points, grades and attributions of AEs that require routine reporting to the Alliance Statistics and Data Center. Questions about routine reporting should be directed to the Data Manager.

Combinations of CTCAE Grade & Attribution Required for Routine AE Data Submission on Case Report Forms (CRFs). Attribution may be secondary to radiation, and/or Mepitel Film.

Of note, pruritus is a common acute toxicity observed secondary to radiation and can also develop in response to Mepitel Film. Based on Mayo institutional experience, pruritus due to Mepitel Film is generally seen within the first week of use.

Attribution	Grade 1	Grade 2	Grade 3	Grade 4	Grade 5
Unrelated			a	a	a
Unlikely			a	a	a
Possible		a	a, b	a, b	a, b
Probable		a	a, b	a, b	a, b
Definite		a	a, b	a, b	a, b

- a) Acute Adverse Events: Other CRF Applies to AEs occurring between registration and within 90 days of the patient's last treatment date, or as part of the Clinical Follow-Up Phase.
- b) Chronic Adverse Events: Late CRF Applies to AEs occurring greater than 90 days after the patient's last treatment date.

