### 7.2 Mepitel Film/standard of care treatment

Patients will be randomized in a 2:1 ratio to receive either Mepitel Film, or the existing institutional standard of care throughout the duration of their radiation. Radiation and protocol directed skin care (standard of care vs Mepitel Film) will be conducted at the registering institution.

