### 7.2.1 Institutional Standard of Care Arm

Patients randomized to the standard of care arm will commence with conventionally fractionated PMRT, with skin management according to their institutional standard of care. Currently, there is no clear standard of care for reducing radiation dermatitis, and clinical practice varies widely across institutions. Patients randomized to this arm, should receive skin management as recommended by their treating physician. To help increase uniformity in the institutional standard of care arm, recommended guidelines for skin care are provided in Appendix IX. We recommend following these guidelines; however, it is not required for participation on this study. Specific skin care products will not be provided for the standard of care arm. Common interventions such as aqueous creams, petroleum ointments, aloe vera, acetic acid soaks, prescription interventions such as mometasone or lidocaine, and

wound care interventions such as Xeroform gauze or silvadene are all permitted. All products used throughout treatment will be recorded for future analyses (Appendix IV). The use of any applied prophylactic barriers including, but not limited to Mepitel Film, Mepitel One, Tegaderm, or Cavilon no sting Barrier Film, is prohibited on this trial. Therapeutic barrier interventions, such as Xeroform, are permitted to treat moist desquamation.

Acquisition of photographs is required for all patients and skin swabs (only for those who provide consent to participate in the optional sub-study). Both initial photos for all patients and skin swabs (for those who consent to participate in the optional correlative substudy) should be acquired no more than 3 days prior to the start of radiation therapy. Immediately upon completion of radiation therapy, the first set of post-treatment photographs and the second set of skin swabs should be acquired.

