# 9.1 Routine Adverse Event Reporting

Adverse event data collection and reporting, which are required as part of every clinical trial are done to ensure the safety of patients enrolled in the studies as well as those who will enroll in future studies using similar agents. Adverse events are reported in a routine manner at scheduled times according to the study calendar in Section 5.0.

**Solicited Acute Adverse Events**: The following adverse events are considered "expected" and their presence/absence should be solicited, and severity graded at baseline, weekly while on treatment, at the 7-14-day post-treatment follow-up, and at the 3-month, 6-month, 1 year and 2-year post-treatment follow-up visits by CTCAE v5.0.

CTCAE v5.0 Term	CTCAE v5.0 System Organ Class (SOC)	PRO-CTCAE term	
Dermatitis radiation	
 
Injury, poisoning and procedural complications
 
	• Itching	
Rash acneiform	Skin and subcutaneous tissue disorders	
 
Radiation skin reaction
 
	
Rash maculo-papular	Skin and subcutaneous tissue disorders	General pain	
• Pruritus	Skin and subcutaneous tissue disorders	Breast swelling and tenderness	
Skin infection	Infections and infestations		

Symptomatic Adverse Events reported by patients through PRO-CTCAE are not safety reporting and may be presented with other routine Adverse Event data.

**Solicited Chronic Adverse Events**: The following adverse events are considered "expected" and their presence/absence should be solicited, and severity graded at the 3-month, 6-month, 1 year and 2-year post-treatment follow-up visits by CTCAE v5.0.

CTCAE v5.0 Term	CTCAE v5.0 System Organ Class (SOC)		
Superficial soft tissue fibrosis	Musculoskeletal and connective tissue disorders		
Fibrosis deep connective tissue	Musculoskeletal and connective tissue disorders		

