#### 12.0 END OF TREATMENT/INTERVENTION

# 12.1 Duration of Protocol Treatment

Radiation therapy is to be given 5 days a week for 5-6 weeks. For patients randomized to Mepitel Film, the film will be applied prior to initiation of radiotherapy and will remain in place for up to 2 weeks following the completion of radiation. Please see the study calendar (Section 5.0) and the treatment section (Section 7.0) for treatment and follow-up time periods (Section 12.3).

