There are two other secondary endpoints that will be evaluated, and both are related to safety. The analysis of these safety endpoints will be based on the safety population, defined as all patients who initiated radiation; further the safety endpoints will be analyzed according to the intervention actually received. The constellation of acute and chronic adverse events (AEs) as scored using the National Cancer Institute Common Terminology Criteria for Adverse Events, v5.0 (CTCAE v5.0) will be summarized within arms by reporting the number and percentage of patients. Specifically, to evaluate the AE profiles associated with each arm, the maximum grade for each type of AE will be recorded for each patient and frequency tables will be reviewed to determine overall patterns. Additionally, the proportion of radiation dermatitis and skin and soft tissue fibrosis using NCI CTCAE v5.0 will be estimated within arms with the exact 95% confidence interval. Given the NCI CTCAE Version 5.0 scales for telangiectasia and hyperpigmentation are developed for total body surface area, they are not applicable to this study. As such, hyperpigmentation and telangiectasia will be evaluated on a 4-point scale, reflecting none, mild, moderate, and severe, and the corresponding number and percentage of patients reporting each will be presented according to arm. To evaluate the impact of chest wall separation on the constellation of AEs, we will display the AE profiles according to chest wall separation (> 25 cm; \le 25 cm) within each arm; additionally, other clinically meaningful separation thresholds will be explored depending on the distribution of the chest wall separation measurements.

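### Section 9.2 names Mepitel Film but not the control arm's skin products as a source of attribution, so unsolicited grade 2 reactions due only to those products need not be reported

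*Combined protocol and SAP*

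**What the plan says.** Section 9.2 sets a grade-by-attribution table for routine reporting. It applies "In addition to the solicited adverse events listed in" Section 9.1, so it governs unsolicited events only. At grade 2 an event is required only when attribution is possible, probable or definite, and then only on the acute form. At grades 3 to 5 the acute form is required on every attribution row, and the Late form only at possible or above. The sources of attribution are given in one sentence: "Attribution may be secondary to radiation, and/or Mepitel Film".

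For the solicited acute terms (radiation dermatitis, acneiform rash, maculo-papular rash, pruritus and skin infection), Section 9.1 says that "their presence/absence should be solicited, and severity graded at baseline, weekly while on treatment", and again at the follow-up visits through two years. It sets no condition on arm or attribution.

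Section 9.0 asks the investigator to attribute each event to protocol treatment. Section 7.2 describes the randomised contrast as follows: "Radiation and protocol directed skin care (standard of care vs Mepitel Film) will be conducted at the registering institution". Section 7.2.1 lists the control-arm options, from moisturisers to prescription topicals, and adds that "wound care interventions such as Xeroform gauze or silvadene are all permitted".

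Acute adverse events are the fifth secondary endpoint (Section 13.5.1). Section 13.5.2 plans, "to evaluate the AE profiles associated with each arm, the maximum grade for each type of AE will be recorded" for each patient, with frequency tables by intervention received.

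**The concern.** The trial compares one skin-care strategy with another, and both can cause reactions of their own. A film-arm event can pass the grade 2 filter as due to radiation or as due to the assigned skin care. On the wording of Section 9.2, a control-arm event can pass only as due to radiation. Plausible examples are skin pain, urticaria, contact or allergic reaction, and blistering, none of which is a solicited term.

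If sites follow the sentence as written, the by-arm tables of these terms compare two collection rules as well as two interventions, and the difference runs against film. An unsubmitted event cannot be added to the CTCAE tables at analysis. If sites instead follow Section 9.0 and count standard skin care as protocol treatment, control-arm capture will vary between sites. Either way the passages need to be reconciled.

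**Working it through.** The plan gives no figure on this point, so there is none to reproduce. The check has two parts.

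**1. Which events the rule treats differently.** The table reads Section 9.1 with the Section 9.2 table, for an event caused by the assigned skin care.

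| Event | Film arm, due to film | Control arm, due to a skin product |
|---|---|---|
| Solicited acute term, any grade | Collected | Collected |
| Unsolicited, grade 1 | Not required | Not required |
| Unsolicited, grade 2, at least possibly due to radiation | Submitted | Submitted |
| Unsolicited, grade 2, due only to the skin care | Submitted | **Not required** |
| Unsolicited, acute, grade 3 to 5 | Submitted | Submitted |

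Only the fourth row differs. The Late form carries the same attribution filter at grades 3 to 5. Whether any late event is lost depends on how footnote (a) is read, because that footnote also covers the clinical follow-up phase.

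**2. How large the gap could be.** Three inputs are needed, and the documents give none of them. All are assumptions:

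- r: true rate of grade 2 reactions to control-arm products, 1% to 10%
- s: share of these that present as a solicited term, 0 to 0.9
- q: share of the remainder rated at least possibly due to radiation, 0 to 0.5

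Control-arm under-count = r × (1 − s) × (1 − q). Multiplying by the 72 planned control patients (Section 13.3) gives the expected number unrecorded:

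| r | s=0, q=0 | s=0, q=0.5 | s=0.5, q=0 | s=0.5, q=0.5 | s=0.9, q=0 | s=0.9, q=0.5 |
|---|---|---|---|---|---|---|
| 1% | 0.72 | 0.36 | 0.36 | 0.18 | 0.07 | 0.04 |
| 5% | 3.6 | 1.8 | 1.8 | 0.9 | 0.36 | 0.18 |
| 10% | 7.2 | 3.6 | 3.6 | 1.8 | 0.72 | 0.36 |

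- Lowest: 72 × 0.01 × 0.1 × 0.5 = 0.04 patients (0.05 percentage points).
- Middle: 72 × 0.05 × 0.5 × 1 = 1.8 patients (2.5 points).
- Highest: 72 × 0.10 × 1 × 1 = 7.2 patients (10 points). This needs a 10% reaction rate, no reaction presenting as rash, pruritus, dermatitis or infection, and none judged possibly due to radiation.

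These are control-arm losses, not net differences between arms. Section 8.1.2 lets film patients use the same products on uncovered skin and after film removal. Reactions to those products meet the same filter, so the film arm loses some events too and the net tilt is smaller.

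**The case against.** The strongest reply is that Section 9.2 is permissive: it says what attribution may be to, not what it must be limited to. Read with Sections 9.0 and 7.2, it could already include control-arm skin care. That reading is open, but nothing tells a site to adopt it, and the sentence that introduces the table names one arm's product and omits the other's.

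It can also be said that most skin reactions reach the database anyway. This is largely right. The solicited list covers the commonest presentations, and many events on irradiated skin may be rated at least possibly due to radiation. The patient and provider mRISRAS items and the PRO-CTCAE items also record pain, itch, burning, desquamation and necrosis weekly in both arms without attribution. They are not CTCAE terms and do not replace the missing records, but they limit what is lost.

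Several stronger readings are tempting, and the documents do not support them:

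- *Control-product reactions are never captured, or the acute profiles as a whole are biased.* Part 1 of the check shows that only one category differs.
- *The documents supply a rate.* Section 7.2.2 puts film intolerance below 10%, and 2 of 33 pilot patients in Appendix I stopped film for pruritus. These figures concern pruritus or rash, which are mainly solicited terms.
- *The gap would produce a spurious significant result.* Section 13.5.2 plans no between-arm test of adverse events.
- *The film arm loses nothing.* Section 8.1.2 rules this out.
- *The 90-day acute window is longer in the film arm,* because Section 12.1 says film "will remain in place for up to 2 weeks following the completion of radiation". Section 12.1 does not define the last treatment date. Footnote (a) in Section 9.2 classifies events by when they occur and also takes in the follow-up phase. Follow-up visits are timed from the end of radiation in both arms.

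**Conclusion.** The point holds in a narrow form. Followed as written, Section 9.2 applies an arm-asymmetric filter to unsolicited grade 2 events due only to the assigned skin care, and the asymmetry runs against film. It is also inconsistent with Sections 9.0 and 7.2. It touches one category of a secondary safety endpoint that is analysed descriptively. The primary endpoint, the solicited terms and acute grade 3 to 5 events are not affected.

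The size cannot be derived from the documents. The range of about 0.04 to 7 of 72 control patients rests wholly on the assumed r, s and q and on sites taking the attribution sentence as a closed list. The direction for this category follows from the text under that reading. The point is a cheap improvement in wording, not a demonstrated bias in the safety results.

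**What to change.** Replace the attribution sentence in Section 9.2 with wording such as: *Attribution may be to radiation and/or to the skin care used (Mepitel Film or standard-of-care products).* Apply it in both arms and on both the acute and the Late forms, and add a matching attribution option to the case report form. Naming the skin care used, rather than the assigned arm, also covers film patients who apply topical products to uncovered skin. It brings Section 9.2 into line with Sections 9.0 and 7.2.

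The cost is one sentence, one form option and a few more grade 2 records, with no added visits or patients. Collecting local grade 2 events regardless of attribution would also remove the asymmetry, but it asks more of sites and is not needed for this purpose.

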# 9.2.1 Non CTCAE Adverse Event Reporting

Because the CTCAE v5.0 does not adequately characterize telangiectasia and hyperpigmentation with respect to the limited field of skin treated on this study, these AEs will be scored using a 4-point scale representing none, mild, moderate, and severe, and recorded separately. Additionally, reconstruction failure and reconstruction complications will be recorded be recorded separately from CTCAE toxicities and are integral to the prespecified secondary endpoints (see Appendix V).

# **List of non-CTCAE events:**

- 1) Telangiectasia (involving skin within radiation treatment field)
- 2) Hyperpigmentation (involving skin within radiation treatment field)
- 3) Reconstruction complications (defined as wound dehiscence, wound infection requiring the administration of oral or IV antibiotics, mastectomy skin flap necrosis, reconstructive flap necrosis not resulting in complete loss of flap, capsular contracture, or implant leakage/rupture/deflation.
- 4) Reconstruction failure (defined as loss of autologous reconstruction/flap, implant explantation, or unplanned expander removal without immediate replacement.

# 9.3 Expedited Adverse Event Reporting (CTEP-AERS)

Investigators are required by Federal Regulations to report serious adverse events as defined in the table below. Alliance investigators are required to notify the Study Chair, and their Institutional Review Board if a patient has a reportable serious adverse event. The descriptions and grading scales found in the NCI Common Terminology Criteria for Adverse Events (CTCAE) version 5 will be utilized for AE reporting. The CTCAE is identified and located on the CTEP website at:

All appropriate treatment areas should have access to a copy of the CTCAE.

For further information on the NCI requirements for SAE reporting, please refer to the 'NCI Guidelines for Investigators: Adverse Event Reporting Requirements' document published by the NCI.

Note: All deaths on study require both routine and expedited reporting regardless of causality. Attribution to treatment or other cause should be provided.

9.3.1 Late Phase 2 and Phase 3 Studies: Expedited Reporting Requirements for Adverse Events that Occur on Studies under an IND/IDE ≤ 30 Days of the Last Administration of the Investigational Agent/Intervention 

# FDA REPORTING REQUIREMENTS FOR SERIOUS ADVERSE EVENTS (21 CFR Part 312)

**NOTE:** Investigators MUST immediately report to the sponsor (NCI) ANY Serious Adverse Events, whether or not they are considered related to the investigational agent(s)/intervention (21 CFR 312.64)

An adverse event is considered serious if it results in **ANY** of the following outcomes:

- 1) Death
- 2) A life-threatening adverse event
- 3) An adverse event that results in inpatient hospitalization or prolongation of existing hospitalization for ≥ 24 hours
- 4) A persistent or significant incapacity or substantial disruption of the ability to conduct normal life functions
- 5) A congenital anomaly/birth defect.
- 6) Important Medical Events (IME) that may not result in death, be life threatening, or require hospitalization may be considered serious when, based upon medical judgment, they may jeopardize the patient or subject and may require medical or surgical intervention to prevent one of the outcomes listed in this definition. (FDA, 21 CFR 312.32; ICH E2A and ICH E6).

ALL SERIOUS adverse events that meet the above criteria MUST be immediately reported to the NCI via CTEP-AERS within the timeframes detailed in the table below.

Hospitalization	• Grade 1 Timeframes	• Grade 2 Timeframes	• Grade 3 Timeframes	Grade 4 & 5 Timeframes
Resulting in Hospitalization ≥ 24 hrs	10 Calendar Days			24-Hour;
Not resulting in Hospitalization ≥ 24 hrs	Not required		10 Calendar Days	5 Calendar Days

**NOTE**: Protocol specific exceptions to expedited reporting of serious adverse events are found in the Specific Protocol Exceptions to Expedited Reporting (SPEER) portion of the CAEPR

# **Expedited AE reporting timelines are defined as:**

- o "24-Hour; 5 Calendar Days" The AE must initially be reported via CTEP-AERS ≤ 24 hours of learning of the AE, followed by a complete expedited report ≤ 5 calendar days of the initial 24-hour report.
- o "10 Calendar Days" A complete expedited report on the AE must be submitted ≤ 10 calendar days of learning of the AE.

Expedited 24-hour notification followed by complete report  $\leq$  5 calendar days for:

<sup>1 Serious adverse events that occur more than 30 days after the last administration of investigational agent/intervention and have an attribution of possible, probable, or definite require reporting as follows:

• All Grade 4, and Grade 5 AEs

# **Expedited 10 calendar day reports for:**

- Grade 2 adverse events resulting in hospitalization or prolongation of hospitalization
- Grade 3 adverse events

# 9.3.2 Expedited AE reporting timelines defined

"24 hours; 5 calendar days" – The investigator must initially report the AE via CTEP-AERS  $\leq$  24 hours of learning of the event followed by a complete CTEP-AERS report  $\leq$  5 calendar days of the initial 24-hour report.

"10 calendar days" - A complete CTEP-AERS report on the AE must be submitted  $\leq 10$  calendar days of the investigator learning of the event.

Any medical event equivalent to CTCAE grade 3, 4, or 5 that precipitates hospitalization (or prolongation of existing hospitalization) must be reported regardless of attribution and designation as expected or unexpected with the exception of any events identified as protocol-specific expedited adverse event reporting exclusions (see below).

Any event that results in persistent or significant disabilities/incapacities, congenital anomalies, or birth defects must be reported via CTEP-AERS if the event occurs following treatment with an agent under a CTEP IND.

Use the NCI protocol number and the protocol-specific patient ID provided during trial registration on all reports.

# 9.3.3 Additional Instructions or Exclusions to CTEP-AERS Expedited Reporting Requirements for Phase 2 and 3 Trials Utilizing an Agent Under a CTEP IND or non-CTEP IND

All adverse events reported via CTEP-AERS (i.e., serious adverse events) should also be forwarded to your local IRB.

Grade 3/4 hematosuppression and hospitalization resulting from such do not require CTEP-AERS but should be submitted as part of study results. All other grade 3, 4, or 5 adverse events that precipitate hospitalization or prolong an existing hospitalization must be reported via CTEP-AERS.

Reporting of cases of secondary AML/MDS is to be done using the NCI/CTEP Secondary AML/MDS Report Form. New primary malignancies should be reported using study Form Notice of New Primary.

Death due to progressive disease should be reported as Grade 5 "Disease progression" in the system organ class (SOC) "General disorders and administration site conditions." Evidence that the death was a manifestation of underlying disease (e.g., radiological changes suggesting tumor growth or progression: clinical deterioration associated with a disease process) should be submitted.

Any death occurring within 30 days of the last dose, regardless of attribution to the investigational agent/intervention requires expedited reporting within 24 hours.

Any death occurring greater than 30 days after the last dose of the investigational agent/intervention requires expedited reporting within 24 hours only if it is possibly, probably, or definitely related to the investigational agent/intervention.

Pregnancy loss is defined in CTCAE as "Death in utero." Any Pregnancy loss should be reported expeditiously, as Grade 4 "Pregnancy loss" under the Pregnancy, puerperium and perinatal conditions SOC. A Pregnancy loss should NOT be reported as a Grade 5 event under the Pregnancy, puerperium and perinatal conditions SOC, as currently CTEP-AERS recognizes this event as a patient death.

A neonatal death should be reported expeditiously as Grade 4, "Death neonatal" under the General disorders and administration SOC.

All new malignancies must be reported via CTEP-AERS whether or not they are thought to be related to either previous or current treatment. All new malignancies should be reported, i.e. solid tumors (including non-melanoma skin malignancies), hematologic malignancies, myelodysplastic syndrome/acute myelogenous leukemia, and in situ tumors. In CTCAE version 5.0, the new malignancies (both second and secondary) may be reported as one of the following: (1) Leukemia secondary to oncology chemotherapy, (2) Myelodysplastic syndrome, (3) Treatment-related secondary malignancy, or (4) Neoplasms benign, malignant and unspecified-other. Whenever possible, the CTEP-AERS reports for new malignancies should include tumor pathology, history or prior tumors, prior treatment/current treatment including duration, any associated risk factors or evidence regarding how long the new malignancy may have been present, when and how the new malignancy was detected, molecular characterization or cytogenetics of the original tumor (if available) and of any new tumor, and new malignancy treatment and outcome, if available.

Treatment expected adverse events include those listed in Section 10.0 and in the package insert.

CTEP-AERS reports should be submitted electronically.

